### 3.10 Data Handling and Record Keeping

Participants' data will be pseudonymised. The study will comply with the Data Protection Act, which requires data to be anonymised as soon as it is practical to do so. A study-specific ID number identifying the participant will be randomly generated. A document matching identity and participant ID will be stored securely in a password-protected file on the Imperial College London computer network drive, only accessed by named research team members. No personal identifiable information will be included in any study electronic database compiled for the purpose of statistical analysis of the research outcomes. Analysis of the data from the study will be undertaken by the lead researcher ([name]).

Data from the questionnaires will be collected using Qualtrics, a research data collection platform (https://www.qualtrics.com/uk/). This data will be stored on a server owned by Qualtrics, whose data storage is compliant with OECD privacy rules and the European Union Directive on Data Protection. Data will be downloaded from

Qualtrics and later stored on Imperial College London's secure network drives. No hard copy of data will be stored.

Smartphone data is uploaded automatically via a secure link (https) to an Imperial College London digital client server (in an ISO 27001 compliant data centre). The data are stored in a dedicated data server in a physically secure, restricted-access environment. Backups are made each night, with a separate full weekly backup. All sources of data are backed up using state-of-the-art encryption technology to protect against the failure of any single hardware device and stored for a minimum of 1 year. Access and transfer logs are kept for two years. Two back-up servers are used and located in physically secure, swipe-card-controlled data centres.

Ethics approval for the pilot study using the earlier version of the app (with the same data storage/transfer aspects) was granted by the Imperial College London Research Ethics Committee (PI: [name]; ICREC 20IC6132).

Imperial College London will keep identifiable information about participants:

- 10 years after the study has finished in relation to data subject consent forms
- 10 years after the study has completed in relation to primary research data following Imperial College London's retention periods.

During this time, the Principal Investigator will be custodian for the data archived following the Imperial College London archiving procedures. The Principal Investigator will preserve the confidentiality of participants taking part in the study and fulfil transparency requirements under the General Data Protection Regulation for health and care research.

Participants will be able to withdraw from the study at any point up until data analysis has commenced by contacting the research team at [contact]. All data will be deleted from Imperial College London network drives. If the participant grants consent, any anonymised data collected up to the point of withdrawal will be used. Participants will not be able to withdraw their data after the results have been published, as data will be anonymous and will not be linked to the participant.

Anonymised data may be made available to other researchers after the end of the study via data repositories such as Open Science Framework and disseminated through peer-reviewed journals and conference presentations. This will be explained to participants in the Participant Information Sheet and Informed Consent form.

#### 3.11 Patient and Public Involvement and Engagement (PPIE)

A Young People's Advisory Group, comprising five young people (4 females and one male) with diverse ages, ethnicities, sexual orientations, and experience with digital mental health interventions, was recruited through social media in 2023. The YPAG has contributed to the design and management of the research during the pilot phase, including informing project documentation, recruitment strategies and app development. The YPAG will be further involved in the main trial to interpret and

disseminate findings. The YPAG will be compensated 25£/hr in accordance with NIHR guidance on PPI. Patient and public involvement activities will be reported using the Guidance for Reporting Involvement of Patients and the Public, Version 2-short version.

### 3.12 Risks and Risk Management

There are no foreseeable serious risks associated with this project. Participants' well-being and safety will be considered a priority concern at all points in the study. However, theoretically, it is possible that a number of procedures (listed below) included in the study may result in (i) revealing elevated mental health risk or (ii) causing increased levels of distress.

If this is the case, the necessary steps to guarantee the participant's well-being and safety will be taken as described below. We will follow Imperial College London's Safeguarding policy.

Study procedures that may result in increased perceived distress include:

- Responding to questionnaires during baseline and outcome assessments
- Self-reporting data and mental health monitoring through the MindCraft app
- Cognitive/behaviour change following MindCraft app use and nudges recommendations

The risk (i), i.e. of revealing elevated mental health risk as measured by high SDQ scores at baseline, will be addressed by putting in place the following series of procedures:

- If the presence of elevated mental health risk is disclosed, the participant will be signposted to specific support resources on managing poor mental health including those to manage suicidal thoughts (https://patient.info/mental-health/depression-leaflet/suicidal-thoughts), as well as additional external sources of support, which will include those listed in the Help section of the MindCraft app (i.e. Shout, YoungMinds, Best For You NHS, and Kooth).

We will also offer participants the option of being contacted by clinicians part of the research team. In case of disclosure of actual or intended harm, in order to protect the immediate safety of the participant, the participant's parents/guardians will be informed by the lead researcher ([name]) via email or phone call. The contact details of the parents/guardians will be provided on the consent-to-contact form.

 In case participants choose to be contacted by the research team, they will be informed that all information is confidential. The limits of confidentiality (e.g. that the researcher may have an ethical duty to disclose information to a third party to protect the immediate safety of the participant or someone else in the rare

circumstance in which it is judged that the participant or someone else is at risk of serious harm) are made explicit to participants in both the Participant Information Sheet and the Consent Form.

The risk (ii), i.e. of distress being caused by the above study procedures, will be minimised in the following ways:

- Participants will be informed about the assessments so that they can prepare themselves and give fully informed consent to participate.
- Trained researchers will oversee the collection of outcome measures and, if needed, consult clinicians on the research team.
- Recommendations delivered through the app will follow evidence-based CBT and behaviour change principles and be approved by clinicians on the research team.
- A safety checklist curated by the clinicians and informed by CBT protocols will be built into the app to ensure that nudges that might be triggering are not shown to vulnerable groups of users.
- In case of worsening of a participant's mental health state for a prolonged period as predicted by the app (e.g. the participant moves from a low-risk to a high-risk SDQ score), the nudges will be disabled by the research team, and participants will be signposted to external sources of support, which will include those listed in the Help section of the MindCraft app (i.e. Shout, YoungMinds, Best For You NHS, and Kooth).
- For participants who score in the high-risk category of the SDQ at follow-up, the participant will be signposted automatically via a link in the online questionnaire to external sources of support, which will include those listed in the Help section of the MindCraft app (i.e. Shout, YoungMinds, Best For You NHS, and Kooth).

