#### Secondary objectives:

- To examine the effectiveness of personalised AI nudges vs non-personalised digital self-help using generic CBT principles vs self-monitoring control on secondary outcomes [Eating Disorder Diagnostic Scale (EDDS); Sleep Condition Indicator Questionnaire (SCI); Self-Injurious Thoughts and Behaviours Interview (SITBI); Self-Efficacy Questionnaire for Children (SEQ-C); World Health Organisation-Five Well-Being Index (WHO-5)] at 1-month follow-up
- To examine the efficacy of personalised AI nudges on improving mental health in CYP in a low-risk group (primary prevention) and reduce poor mental health in a high-risk group (secondary prevention) at 1-month follow-up
- To explore potential mediators and moderators of beneficial effects of Al nudges

**Hypothesis**: Al nudges will be more effective than non-personalised digital self-help using generic CBT principles (active control group) and self-monitoring control at reducing CYP SDQ scores at 1-month follow-up

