### 3.6 Baseline and Follow-Up Assessments

The baseline assessment consists of web-based self-reported validated mental health measures and demographic information (see Outcomes):

- Screening Measures: Mood Disorder Questionnaire (MDQ); Screening to Brief Intervention (S2BI). MDQ and S2BI questionnaires will be used to characterise the sample.
- Primary Outcomes: Strengths and Difficulties Questionnaire (SDQ)

- Secondary Outcomes: Eating Disorders Diagnostic Scale (EDDS); Sleep Condition Indicator Questionnaire (SCI); Self-Injurious Thoughts and Behaviours Interview (SITBI); Self-Efficacy Questionnaire for Children (SEQ-C); World Health Organisation- Five Well-Being Index (WHO-5)
- Demographics: age, gender, sexual orientation, ethnicity, education level, socioeconomic status, location (school)
- Presence of learning difficulties, organic brain disease, or severe neurological impairment that prevents independent use of smartphone app (yes/no)

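### Signposting in section 3.12 is keyed to the SDQ, so a participant who reports self-harm on the SITBI but has a lower SDQ score has no assured signposting

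*Protocol*

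**What the plan says.** Section 3.12 of the Protocol separates two risks: (i) that the study reveals elevated mental health risk, and (ii) that its procedures cause distress.

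The baseline steps are introduced as addressing "The risk (i), i.e. of revealing elevated mental health risk as measured by high SDQ scores at baseline". Beneath that lead-in, the first step reads: "If the presence of elevated mental health risk is disclosed, the participant will be signposted to specific support resources". Two further provisions follow: "We will also offer participants the option of being contacted by clinicians part of the research team", and a clause beginning "In case of disclosure of actual or intended harm, in order to protect the immediate safety of the participant", under which the lead researcher informs parents or guardians by email or phone.

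Under risk (ii), the last step covers follow-up: "For participants who score in the high-risk category of the SDQ at follow-up, the participant will be signposted automatically via a link". The link leads to external support, including the organisations listed in the app's Help section. The same list says: "Trained researchers will oversee the collection of outcome measures and, if needed, consult clinicians on the research team".

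Self-harm is measured separately. The secondary objectives in section 2 include "Self-Injurious Thoughts and Behaviours Interview (SITBI); Self-Efficacy Questionnaire for Children (SEQ-C); World Health Organisation-Five Well-Being Index (WHO-5)] at 1-month follow-up", and section 3.6 lists the same instrument in the baseline assessment. Section 3.7 explains that only the non-suicidal self-injury section is used, reworded so that it covers self-harm of any intent.

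**The concern.** The trial puts a direct question about self-harm to 14- to 19-year-olds at two time points, but its signposting rules are written around another questionnaire. A young person can report self-harm on the SITBI and still score below the high-risk SDQ category. That person meets no explicit signposting trigger.

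The mode of collection makes this matter more. In remote mode the forms are completed from an emailed Qualtrics link (section 3.5). Answers are given under a study ID, and the file matching IDs to identities is held separately (section 3.10). Any human response therefore needs someone to look at the answer and link it back to a person. A link built into the questionnaire needs neither and acts as soon as the answer is given. It is the only step section 3.12 describes as automatic, and a self-harm answer does not set it off.

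The point concerns participant safety. It does not affect the treatment estimate, and no difference between arms is alleged.

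**Working it through.** No arithmetic beyond counting applies. The check sets each signposting or escalation step in section 3.12 against the self-harm measure.

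**Inputs**

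- Self-harm measure: the SITBI section, at baseline (section 3.6) and at 1 month (section 2), covering self-harm of any intent (section 3.7).
- SDQ content: section 3.7 lists five scales (emotional, conduct, hyperactivity/inattention, peer relationships, prosocial). Self-harm scales among them: 0 of 5. A high-risk SDQ score therefore cannot be assumed to pick up a self-harm report.

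**Steps in section 3.12**

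| Step | Stated trigger | Action | Names the SITBI? |
|---|---|---|---|
| Baseline signposting | Elevated risk disclosed, under a lead-in defining the risk by high SDQ | Signposting to support resources | No |
| Offer of clinician contact | None of its own; follows the baseline signposting step | Optional contact | No |
| Harm disclosure | Actual or intended harm, with no SDQ condition | Parents or guardians informed | No |
| Worsening during the study | Prolonged worsening predicted by the app; the example is a move from low-risk to high-risk SDQ | Nudges disabled, signposting | No |
| Follow-up link | High-risk SDQ category | Automatic signposting in the questionnaire | No |

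Two of these are signposting rules that refer to SDQ scores for a set assessment: baseline and follow-up. Of those 2, 0 name the SITBI. The worsening step also signposts, but it rests on the app's prediction rather than on a SITBI answer, so it does not change the result.

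**Applying the rules to the case at issue** (self-harm reported on the SITBI, SDQ below the high-risk category)

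1. *Follow-up.* The condition for the automatic link is not met, so the link does not appear.
2. *Baseline.* The signposting step acts when elevated risk is disclosed, which could be read to include a SITBI answer. The lead-in above it defines the risk by high SDQ, which points the other way. Signposting is possible but not assured.
3. *Harm disclosure.* The clause may apply. However, the text does not say whether a questionnaire answer is a disclosure, and the action is to inform parents or guardians, not to signpost the young person.

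**Number affected.** This is the number reporting self-harm with an SDQ score below the high-risk category. The protocol gives no self-harm rate, so the number cannot be calculated.

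**The case against.** The strongest counter-argument is that section 3.12 already responds to self-harm. The harm clause has no SDQ condition, a SITBI report is a natural reading of actual harm, and informing parents or guardians is a stronger response than a link. This stands in part: it would be wrong to say that self-harm gets no response. It does not supply signposting to the young person, and it leaves open whether a questionnaire answer triggers it.

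Second, the baseline wording is broader than its lead-in. The operative step turns on disclosure, its resources include material on suicidal thoughts, and the section opens without an SDQ qualifier. This also stands in part. The baseline text is ambiguous rather than plainly restrictive, which is why the conclusion there is only that signposting is not assured. The follow-up step has no such ambiguity about its trigger. It does not expressly exclude anyone, but it provides the link for no one else.

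Third, the practical loss may be small. The organisations behind the link are already in the app's Help option (section 3.3), all three arms use the app, trained researchers oversee outcome collection, and the institution's safeguarding policy applies. All of this is true, but the Help list is passive, and the researchers' role is listed under distress caused by procedures, with no stated trigger. The safeguarding policy and the Qualtrics build are not available for review and might contain a self-harm branch. If so, section 3.12 should say so.

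Finally, the counts above describe the wording only and do not measure how many participants are affected. That is accepted.

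**Conclusion.** The concern holds. As written, a participant who reports self-harm on the SITBI and scores below the high-risk SDQ category receives no automatic signposting at follow-up and no assured signposting at baseline. The follow-up part rests on the plain wording of the step; the baseline part rests on reading the steps under their SDQ lead-in.

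The conclusion assumes that section 3.12 is followed as it stands and that no self-harm trigger has been built into documents or forms not shown. The size is unknown for want of a self-harm rate. There is no consequence for bias, power or the primary estimate. It should be fixed because the population is young, the question is asked of everyone, and the remedy is small.

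**What to change.** Make two wording changes in section 3.12:

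- In the lead-in to risk (i), define elevated risk at baseline as a high SDQ score **or** a report of self-harm on the SITBI.
- In the last step under risk (ii), extend automatic signposting at follow-up to participants in the high-risk SDQ category **or** reporting self-harm on the SITBI.

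Use the questionnaire link already described for follow-up, and offer clinician contact after a SITBI self-harm report at either time point. Apply both identically in all three arms.

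The team's clinicians should set the recall window that counts as a positive answer, for example the past month at follow-up, so that a single lifetime episode does not trigger the step twice.

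The cost is a short protocol amendment, one additional branch in the existing Qualtrics form, and some clinician time for participants who accept the offer of contact.

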#### 4. PARTICIPANT ENTRY

#### 4.1. PRE-REGISTRATION EVALUATIONS

N/A

#### 4.2. INCLUSION CRITERIA

- Young people (aged 14-19) in years 10 to 13 attending any school in the United Kingdom that has been approached
- Sufficient English to allow completion of experimental measures and use of the app
- Access to an iOS or Android-compatible smartphone with an embedded activity monitor
- Have the capacity to consent (if over 16 years old)
- Have the capacity to assent and seek consent from parents/guardians (if under 16 years old)

#### 4.3. EXCLUSION CRITERIA

- Have learning difficulties, organic brain disease, severe neurological impairment that prevents independent use of smartphone app

#### 4.4. WITHDRAWAL CRITERIA

Participants will be able to withdraw from the study at any point up until data analysis has commenced by contacting a member of the research team via email at [contact]. Any anonymised data collected up to the point of withdrawal will be used.

#### 5. ADVERSE EVENTS

#### 5.1. **DEFINITIONS**

**Adverse Event (AE):** any untoward medical occurrence in a patient or clinical study subject.

Serious Adverse Event (SAE): any untoward medical occurrence or effect that:

- Results in death
- Is life-threatening refers to an event in which the subject was at risk of death at the time of the event; it does not refer to an event which hypothetically might have caused death if it were more severe
- Requires hospitalisation, or prolongation of existing inpatients' hospitalisation
- Results in persistent or significant disability or incapacity
- It is a congenital anomaly or birth defect

Medical judgment should be exercised in deciding whether an AE is serious in other situations. Important AEs that are not immediately life-threatening or do not result in death or hospitalisation but may jeopardise the subject or may require intervention to prevent one of the other outcomes listed in the definition above should also be considered serious.

#### 5.2. REPORTING PROCEDURES

All adverse events should be reported. Depending on the nature of the event, the reporting procedures below should be followed. Any questions concerning adverse event reporting should be directed to the Chief Investigator in the first instance.

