### 3.2 Randomisation, Intervention Delivery and Masking

Participants will be randomised (in a 1:1:1 ratio) to the three intervention arms and will be instructed to record data every day for four weeks. Stratification will be accounted for by considering SDQ scores to ensure balanced distribution of baseline characteristics.

Randomisation will be undertaken using a computer-based randomisation tool or software platform designed for clinical trials (such as https://www.sealedenvelope.com), ensuring unbiased allocation of participants across the three arms. Randomisation will be independent of the lead researcher.

Participants in the intervention and active control groups and the outcome assessor will be blind to intervention allocation.

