Participants will be followed up at 1 month. If data collection is carried out remotely, baseline and follow-up measures will be collected via an online Qualtrics questionnaire sent to the participant's email. If data collection is carried out in person, participants will complete the baseline (and follow-up) questionnaires through a Qualtrics link (separate from the Consent Form) on their mobile phones.

Completion of the baseline and outcome assessments should take a maximum of 30 minutes. No identifiable information will be collected. Participants will be assigned a unique participant ID, which they will use to complete the baseline and follow-up assessments and sign in to the study app (see Data Management section). Based on their ID, participants will be randomised to different versions of the MindCraft app (see Randomisation).

Reimbursement will be provided upon completion of the study, with the mode of reimbursement determined by each participating school. Schools may choose to distribute vouchers to students or receive the funds centrally to support researchand mental health—related activities, such as travel for workshops at Imperial.

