#### Primary outcome measures

The Strengths and Difficulties Questionnaire (SDQ) (Goodman et al., 1998) is a brief behavioural screening questionnaire used in 2-17-year-olds. It consists of 25 items divided between 5 scales: emotional symptoms (5 items), conduct problems (5 items), hyperactivity/inattention (5 items), peer relationship problems (5 items), and prosocial behaviour (5 items). The first 20 items are added together to generate a total difficulties score. In low-risk or general population samples, an alternative three-subscale version of the SDQ can be used, divided into 'internalising problems' (emotional + peer symptoms, 10 items), 'externalising problems' (conduct + hyperactivity symptoms, 10 items) and the prosocial scale (5 items).

Secondary outcome measures

- The Eating Disorder Diagnostic Scale (EDDS) (Stice et al., 2000) is a 22-item self-report tool designed for individuals aged 13 to 65 that simultaneously assesses diagnostic symptoms of anorexia nervosa, bulimia nervosa, and binge-eating disorder by asking about body image, eating patterns, and compensatory behaviours over the past 3 to 6 months. Items use a combination of Likert, yes-no, frequency, and write-in response formats.
- The Sleep Condition Indicator Questionnaire (SCI) (Espie et al., 2014) is an 8item rating scale measuring sleep problems. The eight items consist of a general
  question on the period of time the individual has had sleep problems. These
  items are rated on a scale from 0 to 4; 4 being the best (e.g., no problem/less
  minutes to fall asleep/very good sleep quality) and 0 being the worst (e.g. >1 year
  sleep problems/more than an hour to fall asleep/very poor sleep quality).
- The Self-Injurious Thoughts and Behaviours Interview (SITBI) (Nock et al., 2007) is a structured interview that assesses the presence, frequency, and characteristics of a wide range of self-injurious thoughts and behaviours, including suicidal ideation, suicide plans, suicide gestures, suicide attempts, and non-suicidal self-injury (NSSI). Only the NSSI section of the interview will be used, modifying the term NSSI to "self-harm" to include all self-harm behaviour regardless of intent.

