#### 5.3.1 Non-serious AEs

All such events, whether expected or not, should be recorded.

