#### 5.3.2 Serious AEs

An SAE form should be completed and emailed to the Chief Investigator within 24 hours

All SAEs should be reported to the Ethics and Research Governance Coordinator where, in the opinion of the Chief Investigator, the event was:

- 'related', ie resulted from the administration of any of the research procedures; and
- 'unexpected', ie an event that is not listed in the protocol as an expected occurrence

Reports of related and unexpected SAEs should be submitted within 15 days of the Chief Investigator becoming aware of the event, using the NRES SAE form for non-IMP studies. The Chief Investigator must also notify the Sponsor of all related and unexpected SAEs.

Local investigators should report any SAEs as required by their Local Research Ethics Committee, Sponsor and/or Research & Development Office.

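### Section 5 requires every adverse event to be recorded, but no listed assessment asks about them and the harm signals already collected are not linked to that duty

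*Protocol*

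**What the plan says.** Section 5 of the protocol sets a complete duty. Section 5.2 says "All adverse events should be reported"; Section 5.3.1 says of non-serious events that "All such events, whether expected or not, should be recorded"; Section 5.3.2 adds that "An SAE form should be completed and emailed to the Chief Investigator within 24 hours". Section 5.1 defines an adverse event broadly, and its definition of a serious one leaves room for medical judgement.

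The scheduled assessments are a baseline and one later point: "Participants will be followed up at 1 month" (Section 3.5). Section 3.6 describes the first: "The baseline assessment consists of web-based self-reported validated mental health measures and demographic information". The instruments named in Sections 3.6 and 3.7 are the MDQ, S2BI, SDQ, EDDS, SCI, SITBI, SEQ-C and WHO-5, with demographics and an eligibility question. For the SITBI, "Only the NSSI section of the interview will be used", reworded to cover self-harm whatever its intent. It is a secondary outcome. Between the two assessments participants "will be instructed to record data every day for four weeks" (Section 3.2).

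Section 3.12 opens with "There are no foreseeable serious risks associated with this project", then lists study procedures that could cause distress, including self-monitoring and change following the nudges. It describes several responses: optional contact from team clinicians, informing parents or guardians when harm is disclosed, disabling nudges and signposting when the app predicts prolonged worsening, and an automatic link to support for a high SDQ score at follow-up.

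**The concern.** A duty to record every event works only if someone is told how events come to light. In a clinic-based trial, staff ask at each visit. Here the participants are school pupils using an app, no named instrument asks the question, and no contact for asking it is scheduled. Section 5 names no collector, time window or form for non-serious events, and it does not refer to the routes in Section 3.12 through which the team would learn that a participant was worse.

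At stake is what the final report can say. The protocol itself names nudges and self-monitoring as possible sources of distress in 14- to 19-year-olds. A short list of adverse events gathered from unsolicited reports could not support a statement that the AI nudges are safe, and a difference in counts between arms could reflect how events were noticed. This has to be fixed before data collection, because no analysis plan can recover events that nobody asked about.

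**Working it through.** **1. Duty against means of detection.** The sources of information after baseline are:

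- *1-month questionnaires (3.5 to 3.7).* They cover symptoms, sleep, eating, self-efficacy, well-being and self-harm. No adverse-event, admission or emergency item is listed. The 1-month form is not itemised separately, so this is read from the instruments named.
- *SITBI self-harm (3.7).* It can show events that may meet the Section 5.1 definition. It is used only as an outcome, with no instruction to log a positive answer.
- *App-flagged worsening (3.12).* The action is to disable nudges and signpost. No adverse-event record is mentioned.
- *High SDQ at follow-up (3.12).* An automatic link is shown. No adverse-event record is mentioned.
- *Disclosed harm (3.12).* Parents or guardians are informed. No link to Section 5 is made.
- *Administrator dashboard (3.3).* It shows usage and nudge ratings, not events.

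No row leads to Section 5.

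**2. Capture by arm.** The app-flagged response consists of disabling nudges and signposting. Sections 3.1 and 3.3 give nudges to the experimental and active-control arms only. Whether a self-monitoring participant who worsens is flagged at all is not stated, so unequal detection is possible. This is an inference from the wording, not a stated difference.

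**3. Who is reached at 1 month.** Inputs from Section 3.8: 505 participants needed, 40% attrition, 842 to be recruited.

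- Reproducing the plan's figure: 505 / (1 - 0.40) = 841.7, rounded up to 842.
- Expected to miss the assessment: 842 - 505 = 337, and 337 / 842 = 40%.

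**4. Illustration with assumed risks.** The protocol gives no event rate. Suppose the true 1-month risk were 2%, 5% or 10%, equal in completers and non-completers:

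- 2%: 842 x 0.02 = 17 participants with an event, of whom 505 x 0.02 = 10 are completers.
- 5%: 842 x 0.05 = 42, of whom 505 x 0.05 = 25 are completers.
- 10%: 842 x 0.10 = 84, of whom 505 x 0.10 = 51 are completers.

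As written, no defined route would record any of these as adverse events. A question asked only on the 1-month form would reach about 60% of them.

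**5. What zero reports would mean.** By the rule of three, zero events among n fully assessed participants puts the upper 95% limit near 3/n. For 281 per arm this is 3/281 = 1.1%; for the 168 expected completers per arm it is 3/168 = 1.8%. If only a fraction c of events is reported, the limit becomes 3/(281 x c). The protocol gives no value of c, so no limit can be stated for unsolicited reports.

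**The case against.** The strongest reply is that participants are not left unobserved. They make daily app entries, prolonged worsening prompts action by the team, clinicians on the team can make contact, parents or guardians are told of disclosed harm, trained researchers oversee outcome collection, and follow-up may take place in person at school. Self-harm and several symptom scales are measured in every arm at 1 month. All of this stands. A reader might infer that nobody is in touch with participants between baseline and 1 month, or that the trial would show almost no harms whatever happened. The documents support neither reading: what is missing is a contact or question meant to elicit adverse events, and the harms most relevant to this app can be compared among completers.

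Three narrower replies also stand. Section 5.1 is broad enough to include self-harm known to the team; Section 5 does not exclude these signals, it only fails to name them. The 40% do have a scheduled contact; they are expected to miss it. And Section 6 reading N/A proves little, since follow-up is described in Section 3.

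A reader might also want to put a figure on the under-reporting. Assuming that 10% to 20% of events are reported, zero reports in 281 would be compatible with a true rate of about 5% to 11% (3/56.2 and 3/28.1). That range follows entirely from a capture fraction with no source in the protocol. It is purely illustrative and should not be used as an estimate.

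None of this supplies an elicitation method or connects the existing signals to Section 5.

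**Conclusion.** The point holds for adverse-event and serious-adverse-event counts. Followed as written, these would rest on unsolicited reports and be under-ascertained to an unknown degree, possibly unequally between the self-monitoring arm and the two nudge arms. It does not extend to all harms, because SITBI self-harm and symptom worsening can be compared by arm among those assessed at 1 month.

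The size of the shortfall cannot be computed from the protocol. The one figure that can is that about 337 of 842 participants are expected to miss the only scheduled post-baseline assessment, if the stated 40% attrition applies to it. The conclusion assumes that the 1-month form contains only the instruments named in Sections 3.6 and 3.7. The change should be made before recruitment to the main trial; it does not call the design or the primary analysis into question.

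**What to change.** - Add one short item, identical in all arms, to the existing 1-month Qualtrics form, asking about any hospital admission, emergency attendance or other serious health event since baseline.
- Send the same single item to those who do not complete the form, since a question on the form alone would miss the expected 337.
- State in Section 5 that self-harm since baseline reported on the SITBI, disclosures under Section 3.12 and app-flagged worsening are logged and reviewed as possible adverse events in all three arms. The protocol gives no SITBI recall period, so the follow-up version needs one that starts at baseline. Say also how worsening is flagged in the self-monitoring arm.
- Report solicited and spontaneous events separately by arm, with the number actually assessed as denominator.
- Show low-to-high SDQ shifts by arm as a descriptive table. Do not class each one as an adverse event, because some will be ordinary score fluctuation.

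The cost is one questionnaire item within the existing 30-minute limit, one short message to non-completers, a paragraph in Section 5 and a safety table. The downside is a few more events for the Chief Investigator to review.
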